The study at hand is an exploratory retrospective study conducted on approximately 1250 patients who received a hemithyroidectomy at the Medical University of Vienna, Department of General Surgery, Division of Endocrine Surgery. A possible confounding factor is that the underlying conditions such as goiter or nodules which lead to the surgery might differ in the patients.

4 Patients

All patients who received a hemithyroidectomy at the Department of General Surgery, Division of Endocrine Surgery between 1994 and 2018 will be included in the study which are around 50 per year totalling around 1250 patients. Due to the study design, no power calculations have been conducted beforehand. However, considering similar studies^{5,6}, this sample size was deemed sufficient in order to achieve valid results and a statistical power of 0.8.

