4.2 Exclusion criteria

- Radiation therapy
- Pregnancy
- Previous thyroid surgery (e.g. nodule removal surgery)

Differences in Levothyroxine requirements after hemithyroidectomy

5 Primary and secondary parameters

The occurrence of post-surgery hypothyroidism and levothyroxine dosage is the primary outcome parameter. The secondary outcome parameter is the timespan between hemithyroidectomy and the need for levothyroxine treatment.

6 Methodology

The list of patients who underwent a hemithyroidectomy will be provided by the IT4Science department via a data extraction from the RDA database. Further information necessary for the analysis (side of hemithyroidectomy, type and dosage of treatment) will be extracted from the AKH-Informationsmanagement (AKIM) at the General Hospital of Vienna (AKH), analyzed and pseudonymized by [name] and, then, safely secured on a server at the Chiari Stoffwechsellambulanz.

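### With no follow-up variable named for extraction, a patient followed or treated elsewhere cannot be told apart from one who never needed levothyroxine

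*Combined protocol and SAP*

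**What the plan says.** - **Population (section 4).** "All patients who received a hemithyroidectomy at the Department of General Surgery, Division of Endocrine Surgery between 1994 and 2018 will be included", described as "around 50 per year totalling around 1250 patients". Sections 4.1 and 4.2 set criteria on age, sex, the operation, radiation therapy, pregnancy and previous thyroid surgery. Neither asks for any postoperative visit, test or length of follow-up.
- **Outcomes (section 5).** The main outcome has two parts: "The occurrence of post-surgery hypothyroidism and levothyroxine dosage is the primary outcome parameter". A time to event is added to these: "The secondary outcome parameter is the timespan between hemithyroidectomy and the need for levothyroxine treatment". No observation window, ascertainment rule or censoring rule is given.
- **Data sources (section 6).** One source identifies the patients: "The list of patients who underwent a hemithyroidectomy will be provided by the IT4Science department via a data extraction from the RDA database". A second supplies the analysis items, namely which lobe was removed, what treatment was given and at what dose; these "will be extracted from the AKH-Informationsmanagement (AKIM) at the General Hospital of Vienna (AKH"). No prescription, insurance, general-practitioner or patient-contact source is named.
- **Analysis (section 6.1).** A multiple logistic regression adjusts for factors such as age, sex, underlying disease and BMI, and a t-test compares dosages. Completeness of follow-up is not mentioned, and there is no rule for a missing outcome.

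**The concern.** Hypothyroidism after hemithyroidectomy may be found, and levothyroxine started, outside the operating hospital. The absence of an entry in that hospital's system is therefore not evidence that the patient stayed euthyroid. The plan takes in all operated patients, reads treatment from one system and names nothing that shows whether a patient was seen again. The analyst then has no basis for separating a true non-event from an unobserved patient.

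Two things are at stake. Section 2 aims to predict whether, at what dose and when levothyroxine is needed. That requires absolute risk, which is too low if unseen patients count as untreated. The right-left comparison also loses power, and it could be distorted if follow-up at the hospital differs by side.

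**Working it through.** **1. The plan's own figures.** The sample size is a count: 50 per year × 25 calendar years = 1250. The power of 0.8 in section 4 cannot be reproduced. Section 4 says that no power calculation was done, and no effect size, right:left split or sidedness is given.

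**2. Reference case.** From the documents: N = 1250, a 22% overall rate (background section), and alpha 0.05 (section 6.1, stated for the dosage test). Assumed: two-sided testing and 625 per side. Power for two proportions is

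Φ[(d − 1.96·SE0)/SE1], with SE0 = √(2·p̄(1−p̄)/n) and SE1 = √([p1(1−p1) + p2(1−p2)]/n).

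Solving for power 0.80 around 22% gives 25.28% versus 18.72%: a difference of 6.6 points, a risk ratio of 1.35 and an odds ratio of 1.47. This is a yardstick, not a target set by the plan.

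**3. Equal loss on both sides, unseen patients counted as untreated.** Observed rate = true rate × (1 − loss). The documents give no loss share, so it is varied. At 30% loss the rates are 17.70% and 13.10%, p̄ = 0.154 and d = 0.0459. SE0 = √(2 × 0.154 × 0.846/625) = 0.0204 and SE1 = 0.0204, so power = Φ(0.29) = 0.61. Starting from the rounded rates 25.3% and 18.7% gives 0.62.

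| Assumed loss | Overall rate | Difference (points) | Risk ratio | Odds ratio | Power, unseen = untreated | Power, unseen excluded |
|---|---|---|---|---|---|---|
| 0% | 22.0% | 6.6 | 1.35 | 1.47 | 0.80 | 0.80 |
| 10% | 19.8% | 5.9 | 1.35 | 1.45 | 0.75 | 0.76 |
| 30% | 15.4% | 4.6 | 1.35 | 1.43 | 0.61 | 0.65 |
| 50% | 11.0% | 3.3 | 1.35 | 1.40 | 0.46 | 0.51 |

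The last column uses n = 625 × (1 − loss) per side with the true rates, so it assumes that loss is unrelated to outcome.

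**4. No true side effect (22% on both sides), unseen patients counted as untreated.**
- Equal loss: the rejection rate stays at 5%.
- Loss of 20% versus 30%: 0.22 × 0.8 = 17.6% and 0.22 × 0.7 = 15.4%. This is a false 2.2-point difference, declared significant about 18% of the time.
- Loss of 20% versus 40%: 17.6% versus 13.2%, declared significant about 58% of the time.

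**5. Dosage.** Unseen treated patients simply drop out of the t-test. At 22% of 1250, 275 are treated; at 30% loss about 193 remain (275 × 0.7 = 192.5). With equal groups, the difference detectable at 80% power is (1.96 + 0.84) × √(2/n per group). It rises from 0.34 SD (n = 137.5) to 0.40 SD (n = 96.25).

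**6. Check on the obvious remedy.** Suppose patients are admitted to the analysis because they have a medication entry, so that cases are seen more readily than non-cases. Take a true 22% on both sides, 90% of cases seen on both sides, and non-cases seen 80% versus 60% (all assumed).
- Restricted rates: 0.198/(0.198 + 0.78 × 0.8) = 24.1% and 0.198/(0.198 + 0.78 × 0.6) = 29.7%. This false 5.6-point difference is declared significant about 49% of the time.
- Counting unseen patients as untreated: 0.22 × 0.9 = 19.8% on both sides, with no false effect.

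Neither coding is safe in every case.

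**The case against.** The strongest reply is that no passage says unseen patients are coded as non-events. They could be left blank and dropped by the regression, and the hospital system may hold treatment started elsewhere and recorded at later visits. This stands: the coding is a likely default, not a stated rule. It does not close the gap, because dropping such patients is equally unwritten and first requires knowing who was not seen.

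The list of items in section 6 may also be incomplete. It omits age, sex, BMI and underlying disease, which section 6.1 needs, and the treatment start date, which section 5 needs. That is fair, but no follow-up variable is named anywhere else either.

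A reader might infer that the side comparison is biased. The documents do not support this. With equal loss the type I error and the risk ratio are unchanged, and the odds ratio, which is what the planned logistic model estimates, barely moves. A false effect needs loss that differs by side, and nothing in the documents shows it. Underlying disease is one conceivable route; section 3 already recognises it as a possible confounder and section 6.1 names it for adjustment.

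Finally, section 3 calls the study exploratory. The reference effect was solved to give 0.80 and the loss shares are assumed, so the power figures are illustrations only.

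**Conclusion.** The gap is real and should be closed before extraction. With the items named in section 6, a patient not treated cannot be told apart from a patient not followed at this hospital. If the unseen count as untreated, incidence is understated in proportion to the loss (22% reads 15.4% at 30% loss) and so is the risk difference. Power falls from 0.80 to between 0.75 and 0.46 as the loss goes from 10% to 50%. These figures rest on an equal split, two-sided 0.05, a reference effect that the plan does not state, and assumed losses.

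Two stronger readings go beyond the text: that the plan codes such patients as not hypothyroid, and that it produces a spurious side effect. The understated incidence matters without either of them, because predicting the need for treatment depends on absolute risk.

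**What to change.** In sections 5, 6 and 6.1:

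- Extract dated postoperative thyroid-function tests and the date of last hospital contact, and state whether the hospital system records treatment started elsewhere.
- Define evaluable patients by any postoperative contact or thyroid-function test within a fixed window, chosen before extraction and applied regardless of treatment status. A medication entry should not by itself make a patient evaluable, since that selects on the outcome.
- Treat patients with no postoperative record as missing for occurrence. In the time-to-treatment analysis, censor untreated patients at last contact.
- Report the number and share evaluable, by side.
- Show the occurrence analysis both ways: evaluable patients only, and all patients with the unseen coded as untreated. State that the restricted analysis assumes follow-up is unrelated to outcome given the covariates.

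The cost is wording, a modest amount of extra extraction, and an analysed number below 1250 that should be reported as such. If loss is unrelated to outcome, excluding the unseen costs no power relative to counting them as untreated (0.65 versus 0.61 at 30% loss).

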6.1 Statistical analysis

The collected data will be analyzed by descriptive statistics and illustrated in SPSS (Version 22) by using graphs, tables and boxplots. All data is password protected and anonymized to ensure adequate privacy protection.

Normally distributed data will be described by calculating median, mean and standard deviation. Patient baseline characteristics will be described as percentages and frequencies for categorical variables or mean and median values and standard deviation for normally distributed continual variables. In order to ensure comparability, a Levene's Test for Equal Variances will be performed. Differences of characteristics between the groups will be analyzed by unpaired T- tests for continuous variables. Possible confounding factors such as age, sex, underlying disease and BMI will be identified and adjusted for in a multiple logistic regression model.

In order to compare the levothyroxine dosages, a parametrical test (t-test) with a significance level of $p < 0.05$ will be performed. Adequate transformations such as the Levene's Test for Equal Variances will be applied to deal with not normally distributed residues and, thus, ensure comparable variances. For illustrational purposes, bar charts, histograms and boxplots will be used.

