Thyroid hormones, thyroxine (T4) and triiodothyronine (T3), are produced in the follicular cells of the thyroid gland and can impact nearly every cell in the human body. They are essential to the human metabolism, influence the basal metabolic rate, bone growth, neural maturation, the body's sensitivity to catecholamines, cell development and differentiation as well as protein, fat and carbohydrate metabolism. With about 5000 µg, the thyroid is the largest storage of T4.^{1(p303)} Therefore, the maintenance of adequate thyroid hormones levels is crucial for the patient's quality of life after a hemithyroidectomy. The thyroid is constituted of a right and a left lobe as well as a connecting isthmus. In most patients, the right lobe is significantly larger than left lobe.² In a 2009 study by Ying and Yung, the right lobe was 6.8ml as opposed to the left lobe with a volume of 5.66ml.³ Although the remaining lobe adapts and continues to grow up to 30% from its original size to compensate for the loss,⁴, thyroid hormone supplementation is required in approximately 22% of all patients after thyroid lobectomy.^{5,6} In order to predict the necessity of thyroid hormone replacement therapy after hemithyroidectomy, risk factors such as a higher TSH before surgery, but also the resected thyroid volume have been identified in the past. Surprisingly, the resected thyroid volume showed significant negative correlation with postoperative TSH levels in a 2015 study by Lee et al.⁵ Previous studies aiming at optimizing post-surgery levothyroxine dosages incorporated sex, age, body surface area (BSA) and body mass index (BMI) but not if the right of left thyroid gland was resected into their calculations.^{7,8} Therefore, the study at hand aims at investigating a possible difference in levothyroxine requirements depending on the side of the resection to ensure adequate treatment.

2 Research questions and aims

- **Research Questions:** We hypothesize a possible influence of right vs left hemithyroidectomy on developing postoperative hypothyroidism as well as treatment dosage.
- **The aim** of this study is to be able to better predict the necessity, dosage and starting point of levothyroxine treatment after a hemithyroidectomy.

3 Study design

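### The adjustment set is left open, year of surgery and preoperative TSH are not named, and levothyroxine dose is compared without any adjustment

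*Combined protocol and SAP*

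**What the plan says.** All references are to the combined protocol and SAP.

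- **Adjustment (6.1 Statistical analysis).** The only statement is: "Possible confounding factors such as age, sex, underlying disease and BMI will be identified and adjusted for in a multiple logistic regression model". How the factors will be identified is not said.
- **Dose (6.1).** For levothyroxine dosage, "a parametrical test (t-test) with a significance level of $p < 0.05$ will be performed". No covariates are attached to this comparison. Section 5 makes dosage part of the primary outcome, together with hypothyroidism.
- **Cohort (4 Patients).** Patients operated on "between 1994 and 2018 will be included in the study which are around 50 per year totalling around 1250 patients". No section sets a follow-up window for recording hypothyroidism or treatment.
- **Confounding foreseen (3 Study design).** "A possible confounding factor is that the underlying conditions such as goiter or nodules which lead to the surgery might differ in the patients". Neither calendar time nor TSH is mentioned there.
- **Known predictors (introduction).** "risk factors such as a higher TSH before surgery, but also the resected thyroid volume have been identified in the past".
- **Extraction (6 Methodology).** "Further information necessary for the analysis (side of hemithyroidectomy, type and dosage of treatment) will be extracted" from the hospital record system. TSH is not in that list.

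**The concern.** This is a non-randomised comparison of right with left resections, so the covariates decide what the side effect means. Three things are left loose.

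1. The set is given by example, so it could be settled after the data are seen.
2. With no follow-up window, a patient operated on in 1994 can have more than 20 years of records and one operated on in 2018 very few. Year of surgery may therefore predict whether treatment is ever recorded. If the share of right-sided operations also moved over the period, part of that trend would appear as a side effect.
3. A logistic model can adjust hypothyroidism (yes or no) but not a dose. For that half of the primary outcome, no adjustment is specified at all.

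Preoperative TSH raises a different issue. The protocol itself treats it as prognostic, and if it is not extracted it cannot be used later.

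**Working it through.** **The plan's own figure.** 2018 − 1994 + 1 = 25 years, and 25 × 50 = 1250. The stated cohort size reproduces.

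**A yardstick.** The plan claims power of 0.8 without an effect size. Assume a 1:1 split, 22% overall (from the introduction: "thyroid hormone supplementation is required in approximately 22% of all patients after thyroid lobectomy") and two-sided 5%. Power of 0.8 at 1250 patients then corresponds to a difference of about 6.6 points (18.7% against 25.3%, odds ratio 1.47).

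**Year of surgery.** The documents give no trend in outcome or in side, so both are assumed. Let recorded risk change by D = 0.22 over the period (12% at one end, 34% at the other). Let the right-sided share change by d around 50%, with no true side effect. With both trends linear and year scaled to u = 0, 1/24, …, 1:

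- Var(u) = (25² − 1)/(12 × 24²) = 624/6912 = 0.0903
- spurious risk difference = D × d × Var(u)/(0.5 × 0.5) = 0.22 × 0.361 × d = 0.0794 d
- standard error = √(2 × 0.22 × 0.78/625) = 0.0234
- type I error = Φ(−1.96 + z) + Φ(−1.96 − z), with z = spurious difference/standard error

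| Drift in side share | Spurious difference | z | Odds ratio | Type I error, formula | Type I error, simulated without year |
|---|---|---|---|---|---|
| 0 | 0 | 0 | 1.00 | 5.0% | 4.5–5.0% |
| 10 points | 0.8 points | 0.34 | 1.05 | 6.3% | 5.3–5.9% |
| 20 points | 1.6 points | 0.68 | 1.10 | 10.4% | 9.7–10.6% |
| 30 points | 2.4 points | 1.02 | 1.15 | 17.4% | 15.8–17.3% |

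The simulated column is the range from two runs of 3,000 cohorts of 1250. Monte Carlo error near 5% is √(0.05 × 0.95/3000) = 0.4 points. With year in the model, simulated type I error was 4.7–5.5% in every scenario, including no drift. Under a milder assumed risk trend (17% to 27%), even a 30-point drift gave only an odds ratio of 1.07 and a type I error of 8.2%. Reversing the direction of either trend changes only the sign of the bias.

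**Preoperative TSH, assumed unrelated to side.** 3,000 simulated cohorts per setting, 625 per side, true risks 18.7% and 25.3%:

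| Assumed TSH odds ratio per SD | Power without TSH | Power with TSH | Standard error of side term, without and with |
|---|---|---|---|
| 1.5 | 80.5% | 81.3% | 0.138, 0.140 |
| 2 | 80.1% | 83.9% | 0.138, 0.144 |
| 3 | 80.4% | 86.9% | 0.138, 0.151 |

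Under the null, rejection was 4.8–5.6% without TSH and 4.5–5.3% with it. The gain of about 1 to 7 points comes from the side odds ratio moving away from 1 (from 1.47 to 1.49–1.59). The standard error does not fall.

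**Dose.** No simulation is needed. Setting section 5 beside 6.1 shows a primary outcome whose only stated test has no covariates. At 22%, about 0.22 × 1250 = 275 patients would be treated. That is ample for a linear model with a few terms, and the same 275 events support two further terms in the logistic model.

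**The case against.** The strongest reply is that 6.1 excludes nothing. Its covariates are examples, so year and TSH could still be added, and the study is declared exploratory. That stands against any reading that the plan fixes a set which leaves these two out. It does not remove the gap: the set remains undefined, and TSH is not on the extraction list.

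A reader might also infer that the side comparison is already confounded by year. The documents do not support this. A confounder must be related to side as well as to outcome, and nothing in them links side to calendar year or to TSH. Unequal follow-up alone does not bias the comparison if the left/right mix is stable. Nor does a change in indications over time establish the point, since underlying disease is already flagged in section 3 and named for adjustment in 6.1.

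Finally, retrieving TSH has a cost. Older records may lack it, and a complete-case model could lose enough patients to cancel a gain of a few points of power. That stands, and it is why a missing-data rule belongs in the fix.

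**Conclusion.** The point holds as a gap in specification with an inexpensive remedy, not as demonstrated bias.

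- **Dose** is the firmest part. It rests on the text alone: no adjustment is specified for half of the primary outcome in a non-randomised comparison.
- **Year** is a safeguard. Its value depends on two assumed trends. The spurious difference is 0.8 points at a 10-point side drift and 1.6 points at a 20-point drift, against the 6.6 points detectable with 80% power. It matters only if the side mix moved substantially and recorded risk also changed strongly over time.
- **TSH** is mainly a question of power, about 1 to 7 points if it is unrelated to side. It would be wrong to say that leaving it out biases the null test or inflates the standard error of the side term.

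**What to change.** 1. Fix the adjustment set in 6.1 before analysis: age, sex, BMI, underlying disease and year of surgery (continuous or in 5-year bands), all kept regardless of p-value.
2. Add preoperative TSH to the extraction list in section 6 and to the model. State a rule for missing values, such as multiple imputation, so that patients are not dropped.
3. Make a linear model for dose, with side and the same covariates, the main dose analysis. The t-test can stay as an unadjusted description.
4. Do not add resected volume to this set by default. The introduction reports that the right lobe is usually larger, so volume may lie on the path from side to outcome, and adjusting for it would change the question.

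**Cost.** Year costs nothing to collect: surgery date defines the cohort and is needed for the secondary outcome. The linear model needs no new data beyond the covariates. TSH needs retrieval for about 1250 patients, with some early values likely to be missing. Adjusting for year reduces the effect of unequal follow-up but does not replace a defined follow-up window.

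### Levothyroxine dose, part of the primary outcome, is compared by side with a t-test without covariates, so no body-size measure enters the dose comparison.

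*Combined protocol and SAP*

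**What the plan says.** The background, ahead of Section 2, motivates the study by noting that earlier dosing work "incorporated sex, age, body surface area (BSA) and body mass index (BMI) but not if the right of left thyroid gland was resected". Section 5 makes hypothyroidism and levothyroxine dosage together the primary outcome, and the null hypothesis in Section 6.1.1 covers both.

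Section 6.1 treats the two parts differently. For adjustment it lists possible confounders "such as age, sex, underlying disease and BMI" and places them in a multiple logistic regression. On dose it says: "In order to compare the levothyroxine dosages, a parametrical test (t-test") at the 0.05 level, with no covariates mentioned. BSA appears only in the background and the abbreviation list.

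The extraction items given as examples in Section 6 are side and the type and dosage of treatment. Height and weight are not named, but neither are age, sex and BMI, so that list is evidently incomplete.

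**The concern.** The study's rationale is to add side of resection to what is already used to calculate dose. The planned dose comparison contains side and nothing else. It therefore cannot show whether side adds anything to the cited inputs, and all dose variation linked to sex, age and body size stays in the error term.

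This matters most for dose because that comparison rests on few patients: about 22% of 1250 if the rate in the background holds. Section 3 also names the underlying condition as a possible confounder, and the t-test leaves that out as well.

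If a dose model is added, the body-size measure has to be chosen. BMI divides height out, so an absolute daily dose that follows body size is only partly captured by it.

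**Working it through.** **The plan's own figures.** About 50 patients a year over 1994 to 2018 (25 calendar years) gives 50 × 25 = 1250, as stated. Section 4 says that "this sample size was deemed sufficient in order to achieve valid results and a statistical power of 0.8", but gives no effect size, dose SD or left:right ratio, so the 0.8 cannot be reproduced. A detectable difference is computed instead.

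**Dose comparison as planned.** Treated patients: 0.22 × 1250 = 275. The plan does not say whether untreated patients enter the comparison; I assume they do not. With a 1:1 split (137.5 per side), two-sided 0.05 and 80% power:

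- detectable difference = (1.960 + 0.842) × √(2/137.5) = 0.338 SD
- at a 1:1.5 split: 0.345 SD

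**Gain from adjusting for body size.** Let R² be the share of dose variance that body size explains. Residual variance falls by a factor 1/(1 − R²), and the detectable difference is multiplied by √(1 − R²). The documents give no R²; 10% to 30% is assumed.

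| R² | Variance factor | Detectable difference (SD) | Power at 0.338 SD | Equivalent extra treated patients |
|---|---|---|---|---|
| 0 (t-test) | 1.00 | 0.338 | 80.0% | – |
| 0.10 | 1/0.90 = 1.11 | 0.321 | 84.0% | 275 × 0.111 ≈ 31 |
| 0.20 | 1/0.80 = 1.25 | 0.302 | 87.9% | 275 × 0.25 ≈ 69 |
| 0.30 | 1/0.70 = 1.43 | 0.283 | 91.8% | 275 × 0.429 ≈ 118 |

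The interval narrows by 1 − √0.90 = 5% to 1 − √0.70 = 16%.

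**How much of this is BSA rather than BMI.** At equal BMI, a patient of 185 cm weighs (1.85/1.60)² = 1.34 times a patient of 160 cm, so BMI does lose information. Sex recovers part of it. In a simulation of 400,000 patients (assumed: 80% women; height 165, SD 6.5 cm in women and 178, SD 7 cm in men; BMI 26, SD 4.8), BMI plus sex explained about 85% of the variance in weight and 75% in BSA. If BSA drives dose, the residual-variance ratio of BMI plus sex to BSA plus sex is (1 − 0.75R²)/(1 − R²):

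- R² = 0.10: 0.925/0.90 = 1.03
- R² = 0.30: 0.775/0.70 = 1.11

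If weight drives dose, the simulated ratio with BSA is 1.01 to 1.05. The range across both cases is 1.01 to 1.11.

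**Cross-check.** A second simulation used 2000 runs of 275 treated patients, dose proportional to BSA, residual SD 25 µg and side independent of body size (all assumed). The SE of the side effect was 3.19 with no covariates, 3.08 with sex, age and BMI, and 3.04 with BSA added. In variance terms the whole gain is (3.19/3.04)² = 1.10, of which BSA on top of BMI gives (3.08/3.04)² = 1.03. Both agree with the R² = 0.10 case. Bias was about 0.1 µg, within simulation noise, and type I error was 4.5% to 4.7% in all three models.

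**The case against.** A reader might infer that the plan takes BMI as its body-size measure for dose and drops BSA. The documents do not support that. The list that names BMI belongs to the logistic model, and the dose comparison has no body-size measure at all. The list also opens with such as, so BSA is unspecified rather than excluded. Nor does anything say that only a BMI value would be stored.

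The strongest case against the point is that the gain rests on an assumed R². The background says only that earlier studies incorporated BSA and BMI, not how well either predicted dose. By their titles, the two cited dosing papers concern thyroidectomy and total thyroidectomy; with one lobe remaining, dose may follow body size less closely. The study is also described as exploratory, and an unadjusted t-test is valid when side is unrelated to the covariates. All of this stands. It limits the size of the gain, but not the fact that a primary outcome is compared without the variables the protocol itself names.

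It can also be said that BSA is not the main omission among cited predictors: "risk factors such as a higher TSH before surgery, but also the resected thyroid volume have been identified in the past", and neither is on the adjustment list. That is fair, but those are cited for the need for replacement rather than the dose. Resected volume may also lie on the path from side to outcome, so it would belong in a separate model.

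**Conclusion.** The point holds as a minor improvement in method. Dose is compared by side without covariates, and a linear model would use the same patients more efficiently. The variance factor is about 1.11 to 1.43 against the t-test if body size explains 10% to 30% of dose variance, and less if it explains less.

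The choice of BSA over BMI is marginal, at 1.01 to 1.11 within that total. No bias from using BMI is shown, because nothing in the documents suggests that body size differs by resected side. Underlying disease is different, since Section 3 itself calls it a possible confounder, but the documents give no figures from which to size its effect on dose.

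**What to change.** In Section 6.1, replace the dose t-test with a linear regression of daily dose (transformed if the residuals require it) on side, age, sex, underlying disease and one body-size measure that retains height: BSA or weight. Report the adjusted side difference in micrograms per day with a 95% CI. The unadjusted comparison can be kept alongside as a sensitivity analysis. BMI can stay in the logistic model for occurrence. In Section 6, name height and weight before surgery as two extraction fields, from which BMI and BSA are both derived.

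The cost is a few lines of text and no measurements beyond those BMI already needs. The downside is missing data: records without height and weight lack the covariate. If a share m of treated patients is dropped for this reason, precision relative to the t-test is (1 − m)/(1 − R²), which falls below 1 once m exceeds R². At R² = 0.10, losing more than 10% of treated patients would cancel the gain. The plan should therefore state how missing height or weight is handled and report how often it occurs on each side.

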6.1.1 Null hypothesis

H₀: The side of the resected thyroid lobe in a hemithyroidectomy does not influence the hypothyroidism occurrence and levothyroxine dosage requirements after surgery.

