6.1.2 Secondary hypothesis

H₀: There are no sex differences between men and women depending on the side of the resected thyroid lobe in the occurrence of hypothyroidism and the needed levothyroxine dosage after a hemithyroidectomy.

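### Levothyroxine dosage, one of the two primary outcome components, gets only an unadjusted t-test, and the sex hypothesis in section 6.1.2 has no planned analysis

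*Combined protocol and SAP*

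**What the plan says.** Section 5 gives the primary outcome two components: "The occurrence of post-surgery hypothyroidism and levothyroxine dosage is the primary outcome parameter". The primary null in section 6.1.1 covers both, stating that side "does not influence the hypothyroidism occurrence and levothyroxine dosage requirements after surgery".

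Section 6.1 deals with the two components differently:

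- **Dosage:** "In order to compare the levothyroxine dosages, a parametrical test (t-test) with a significance level of" 0.05. No covariate is mentioned. The sentence on transformations that follows concerns distribution and variance, not confounding.
- **Confounders:** age, sex, BMI and underlying disease "will be identified and adjusted for in a multiple logistic regression model". The outcome of that model is not named.

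Section 3 describes an exploratory retrospective study and warns: "A possible confounding factor is that the underlying conditions such as goiter or nodules which lead to the surgery might differ in the patients". The introductory text before section 2 reports that earlier dosing studies used sex, age, BSA and BMI, but not the side resected. Section 2 says the aim "of this study is to be able to better predict the necessity, dosage and starting point of levothyroxine treatment after a hemithyroidectomy".

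Section 6.1.2 adds a secondary null: "There are no sex differences between men and women depending on the side of the resected thyroid lobe in the occurrence of hypothyroidism", and extends it to the dose needed. In section 6.1, sex appears only as an example of a confounder.

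**The concern.** Left and right hemithyroidectomy patients were not allocated at random, and the plan itself lists factors it thinks need adjustment. It provides that adjustment in a model form that suits occurrence of hypothyroidism but not a continuous dose. Followed literally, one of the two primary components would be reported unadjusted. The study's stated contribution is to add side to the factors already used for dosing, and a two-group test cannot show what side adds to them.

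For 6.1.2, entering sex as a main-effect covariate does not test whether the side effect differs between men and women. Nor does it compare the sexes within each side. A stated hypothesis would reach the report with no pre-planned test, so any test would be chosen after the data are seen.

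**Working it through.** **Matching questions to analyses**

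| Question | Where stated | Analysis planned in 6.1 |
|---|---|---|
| Side and occurrence | 5, 6.1.1 | Logistic model with covariates (the natural reading) |
| Side and dose | 5, 6.1.1 | t-test, no covariates |
| Sex and side, occurrence | 6.1.2 | None |
| Sex and side, dose | 6.1.2 | None |

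No linear regression, analysis of covariance, interaction term or sex-stratified comparison appears anywhere. The finding rests on this table; the figures below only give it scale.

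**Inputs.** From the documents: about 50 patients a year over 1994 to 2018, and about 22% needing supplementation. The headcount reproduces: 50 × 25 = 1250. The stated power of 0.8 can be neither reproduced nor refuted, because no effect size, dose SD or left/right split is given. Assumed here: two-sided 5% level, 80% power (multiplier 1.96 + 0.84 = 2.80), equal side split, 50% to 80% women, and covariates explaining R² = 0.1 to 0.4 of dose variance.

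**Dose, side effect, treated patients only.** Treated = 0.22 × 1250 = 275, or 137.5 per side.

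- Unadjusted: SE = √(2/137.5) = 0.1206 SD; detectable difference 2.80 × 0.1206 = 0.338 SD.
- Adjusted: SE × √(1 − R²) = 0.1144 (R² 0.1) and 0.0934 (R² 0.4), so 5% to 23% smaller; detectable 0.321 and 0.262 SD.
- Equivalent sample: 275/(1 − R²) = 306 and 458.
- With a 60:40 side split: 0.345 SD unadjusted, 0.327 and 0.267 SD adjusted.

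If all 1250 patients were analysed, with untreated patients at zero dose, the unadjusted figure would be 2.80 × √(4/1250) = 0.158 SD.

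**What confounding could do (illustration only).** Rejection rate under the null = P(|Z + shift/SE| > 1.96). An assumed left-right shift of 0.04 to 0.08 SD from covariates raises the nominal 5% to about 6% to 10% with 275 patients, and to about 11% to 29% with 1250. A zero shift leaves it at 5%.

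**Side-by-sex contrast.** SE = √(sum of 1/cell size).

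- Dose, 275 treated: 50% women gives four cells of 68.75, SE 0.241, detectable 0.68 SD. With 80% women, cells of 110, 110, 27.5 and 27.5 give SE 0.302, detectable 0.84 SD. Adjusted: 0.64 and 0.80 SD at R² 0.1; 0.52 and 0.65 SD at R² 0.4.
- Dose, all 1250: 0.32 to 0.40 SD unadjusted.
- Occurrence, 1250 at 22%: SE on the log-odds scale = √(sum of 1/(cell size × 0.22 × 0.78)) = 0.273 and 0.341. The detectable ratio of odds ratios is exp(2.80 × SE) = 2.15 and 2.60.

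**Behaviour of the proposed model.** In 5000 simulated datasets of 275, with side independent of covariates, no true effect and HC3 standard errors, rejection at the 5% level was 0.044 to 0.051 for side and 0.045 to 0.054 for side-by-sex. This shows correct error rates when there is no confounding; it is not evidence about confounding.

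**The case against.** The logistic sentence names no outcome, so logistic may be a slip for regression in general, or dose may be meant to be dichotomised. The plan says neither. If it is a slip, the wording needs the same repair.

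The harm is not demonstrated. Section 3 says conditions may vary among patients, not between left and right, and the dosing studies cited in the introduction concern, by their titles, thyroidectomy and total thyroidectomy. This stands: the bias may be nil, and the R² range is an assumption.

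Section 6.1 also plans t-tests of continuous characteristics between groups, so an imbalance in age or BMI would probably be noticed. That is a real safeguard, but a partial one. Categorical characteristics such as sex and underlying disease are only described, and noticing an imbalance does not correct the dose result.

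Section 6.1.2 is ambiguous. It could mean sex differences within each side, and the t-test sentence names no groups. Even so, no within-side sex comparison is planned, so neither reading has a test. The study is exploratory and the contrast has little power. That supports labelling the test exploratory, not leaving a stated null without one.

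**Conclusion.** The concern holds on the text, with high confidence, and should be fixed. One of the two primary components has no adjusted analysis in a non-randomised comparison, and the 6.1.2 null has no planned analysis for either outcome.

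The direction and size of any confounding cannot be derived. If covariates are balanced by side, the t-test is unbiased and the cost is precision: a detectable difference of 0.34 SD instead of 0.32 to 0.26 SD among 275 treated patients, under the assumed R² and an equal side split. If they are not balanced, the plan has no dose analysis that corrects for it. The interaction can detect only large effects (0.68 to 0.84 SD unadjusted among the treated; a ratio of odds ratios of about 2.1 to 2.6 for occurrence) and should be treated as exploratory.

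**What to change.** In section 6.1:

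1. Make the main dosage analysis a linear regression of dose on side, with age, sex, BMI and underlying disease as covariates and robust standard errors. Report the adjusted left-right difference with a 95% CI. Keep the t-test as the unadjusted comparison.
2. State that the logistic model is for occurrence of hypothyroidism.
3. Add a side × sex term to both models and report the side effect in men and in women with CIs, labelled exploratory. State which reading of 6.1.2 is meant; the same models also give the sex difference within each side.

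The cost is a few lines of wording and SPSS syntax, using covariates the plan already names. There are three limits:

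- **Missing covariates.** In a complete-case analysis the SE relative to the unadjusted test on all treated patients is √((1 − R²)/(1 − m)), where m is the share missing. The precision gain is gone once m equals R². At R² 0.1 and m 0.3 the SE is √(0.9/0.7) = 1.134 times as large, that is 13% larger.
- **Choice of dose population.** Treated-only analysis conditions on a post-surgical event that side may influence, while entering zeros mixes occurrence with dose. Covariate adjustment is not shown to settle this trade-off, which is for the investigators. A treated-only result should be read alongside occurrence and not as causal.
- **Low interaction power.** Those estimates will be mainly descriptive.
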